
Primary Objectives:
 
 • To determine the safety and tolerability of three different doses of intranasal insulin in patients with Parkinson's disease (PD) 	

Secondary Objectives:
 
 • To evaluate efficacy of intranasal insulin on cognitive functioning in PD • To evaluate efficacy of intranasal insulin on motor function in PD • To evaluate efficacy of intranasal insulin on mood and apathy in PD • To identify which outcome measures are most sensitive to effects of intranasal insulin in PD 	
STUDY DESIGN	
Study Type	Dose-finding
Control Type	None
Study Indication Type	Dose-finding, safety
Blinding Schema	Double blinded
Device	SipNose nasal device
Study Design	randomized, parallel-group, double blind, placebo-controlled
Planned Duration of Subject Participation	8 weeks (Treatment duration: 3 weeks)
PRIMARY ENDPOINTS	

 • Composite safety event of either: a reduction of fasting glucose to <70 mg/dL or an unintended reduction of weight >5% • Pre-post change in safety measures (fasting glucose and weight) • Number of AEs and SAEs 	
SECONDARY ENDPOINTS	

 • Pre-post change in cognitive function measures 	

 • Pre-post change in motor function measures • Pre-post change in mood and apathy measures 	
INVESTIGATIONAL PRODUCTS, DOSE AND MODE OF ADMINISTRATION	
Investigational Product	
Regular insulin (Novolin-R) in 3 different doses and placebo
 
Dose 1, group with 7 participants: 20 IU/IN (10 units IN in one nostril twice daily x 21 days, volume 100 µl)
 
Dose 2, group with 7 participants : 40 IU/IN (10 units IN in each nostril twice daily x 21 days, volume 100 µl)
 
Dose 3, group with 9 participants: 80 IU/IN (20 units IN in each nostril twice daily x 21 days, volume 200 µl)
 
Dose 4, group with 7 participants: placebo (each nostril, twice daily)

SUBJECT SELECTION	
Targeted Accrual	30 subjects. We estimate a need to consent 50 participants in order to reach this goal.
INCLUSION CRITERIA	

 1. Subject has Idiopathic PD defined by the cardinal sign, bradykinesia, plus the presence of at least 1 of the following: resting tremor or rigidity and without any other known or suspected cause of Parkinsonism (according to MDS clinical diagnostic criteria for Parkinson's disease- Postuma et al, Movement Disorders 2015), confirmed by a fellowship trained movements disorder specialist 2. Subject is Hoehn & Yahr stage less than or equal to 3 3. Subject has a MOCA score ≥16. 4. Subject is > 40 and <90 years of age. 5. Female subjects are post-menopausal or have a negative pregnancy test 6. The subject must be proficient in speaking, reading and understanding English in order to comply with procedural testing of cognitive function, memory and physiology. 7. Subject has provided informed written consent prior to participation. In the event that subject is legally unable to provide informed written consent due to deterioration in cognitive abilities, fully informed written consent must be provided by a legally authorized representative. 8. Subject is on a stable dose (at least 1 month prior to baseline visit) of antiparkinsonian agents and is willing to remain on this dose for the duration of the study. If the subject is on a cholinesterase inhibitor, a stable dose without changes for 1 month is also required. 9. Subject has undergone a brain CT or MRI prior to the study as part of their previous diagnostic workup for PD to rule out underlying structural lesions, as determined clinically significant by the investigator 	

EXCLUSION CRITERIA

1. Subject has atypical Parkinson's syndrome(s) due to drugs (e.g., metoclopramide, neuroleptics), metabolic neurogenetic disorders (e.g., Wilson's Disease), encephalitis, cerebrovascular disease, or degenerative disease (e.g., Progressive Supranuclear Palsy, Multiple System Atrophy, Corticobasal Degeneration, Lewy Body dementia)
2. Subject has medical history and/or clinically determined disorders: chronic sinusitis, untreated thyroid disease, or significant head trauma.
3. Subject has history of any of the following: moderate to severe pulmonary disease, poorly controlled congestive heart failure, significant cardiovascular and/or cerebrovascular events within previous 6 months, condition known to affect absorption, distribution, metabolism, or excretion of drugs such as any hepatic, renal or gastrointestinal disease or any other clinically relevant abnormality that inclusion would pose a safety risk to the subject as determined by investigator.
4. Subject has had previous nasal and/or oto-pharyngeal surgery and severe deviated septum and/or other anomalies.
5. Subject has history of any psychiatric illness that would pose a safety risk to the subject as determined by investigator.
6. Subject is currently taking sedative medications that are clinically contraindicated as determined by investigator.
7. Subject has undergone a recent change (<1 month) in their anti-parkinsonian medication, cholinesterase inhibitor or anti-depressant medication.
8. Subject has current or recent drug or alcohol abuse or dependence as defined by DSM-IV TR.
9. Screening laboratory results that are medically relevant, in which inclusion would pose a safety risk to the subject as determined by investigator.
10. Subject has participated in a clinical trial investigation within 3 months of this study.
11. Subject has an insulin allergy.
12. Subject has Insulin-dependent diabetes

DEFINITIONS

Adverse event (AE)	Any undesirable patient experience that may include but is not limited to an abnormal sign, symptom, illness, abnormal laboratory value, or other medical event.
Data Safety Monitoring Board (DSMB)	An independent group assigned to review safety data to monitor for incidence of trends that would warrant termination of the trial.
Hoehn and Yahr scale	Commonly used scale for describing progression of Parkinson's symptoms, ranging from 1 (unilateral symptoms only) to 5 (wheelchair bound or bedridden)
Intranasal (IN)	A method of drug delivery that is particularly applicable to delivering centrally acting medications into the central nervous system.
Montreal Cognitive Assessment (MoCA)	Brief 30-point cognitive screening measure that has been validated for use among individuals with Parkinson's disease.
Serious adverse events (SAE)	Any symptom, sign, illness or experience that develops during the study and results in a life-threatening situation, hospitalization, significant disability, and other events determined by the investigator to be significant.
United Parkinson's Disease Rating Scale (UPDRS)	Is the most widely used clinical rating scale for Parkinson's disease. Part III of the rating scale evaluates motor symptoms in Parkinson's disease (PD)

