4.3 Safety

- Incidence and severity of serious adverse events (SAEs) and adverse events (AEs)
- Frequency of change in clinically-significant vital signs, physical exam or neurological exam
- Plasma glucose level <70mg/dl
- Change in weight

5 Study Design

This study is a single center trial to determine dose finding, safety and tolerability of 3 doses of intranasal (IN) regular insulin (Table #2) and placebo in patients with Parkinson's disease.

Table 2: Intranasal Drug Dosing

Group	Drug	Dose	Volume	N=
Dose group 1	Insulin	20 IU/IN (10 IU, one nostril, twice daily)	100µl	7
Dose Group 2	Insulin	40 IU/IN (10 IU, each nostril, twice daily)	100µl	7
Dose Group 3	Insulin	80 IU/IN (20 IU, each nostril, twice daily)	200µl	9
Dose Group 4	Placebo	0.9% Saline (each nostril, twice daily)	200µl	7

After written informed consent has been obtained from the subject and family member/caregiver, subjects will be screened to assess study eligibility based on study inclusion/exclusion criteria. Subjects who are eligible at the end of the screening visit (Visit 1) will be scheduled for a baseline and randomization visit (Visit 2). During the baseline visit, subjects will be administered a cognitive battery. Subjects will also undergo a neurological examination, including the UPDRS (United Parkinson's Disease Rating Scale- MDS) to be performed in the "ON-STATE" (after taking Anti-Parkinson's medications according to the subject's regular medication schedule). A final safety/assessment visit will take place 3 weeks after visit 2 at which time the tests will be re-administered.

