12.1 Statistical Analysis Overview

Due to the small sample size of this study, statistical analysis will be mainly exploratory and descriptive: t-tests (or Mann-Whitney u-tests if normality of the data is not met) are used to compare the difference of a continuous measure between groups (such as patient age at baseline, various efficacy measures), and contingency tables and chi-square tests are used to compare the difference of a categorical variable (such as patient gender at baseline, various safety and adverse events).

To minimize the potential confounding effects of gender and MOCA score on the treatment effect, we will use stratified block randomization when assigning patient to one of the four study groups. The stratification factors will be gender (male/female) and MOCA score (low <22/30 and high>23/30). We will use block size of four.

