12.2 Statistical Analysis of Primary Aim – safety, tolerability and adverse events

To assess safety and tolerability of the study drug at varying dose levels, AEs and SAEs will be categorized and summarized by study group. We will descriptively note if any group was more likely to have experienced a particular AE/SAE or generally experienced more AEs/SAEs throughout the course of the study; if we notice a significant ‘spike’ associated with a particular dosing group for a certain event, we’ll construct a chi-square test to see if it’s statistically significant. We will also assess the number of and reason for early withdrawals in each study group.

We will also monitor two key safety measures: 1) a fasting glucose < 70 mg/dL and 2) an unintended weight loss of >5% (relative to the patient’s weight at visit 2). The number of participants in each group who experience either or both of these events will be counted and descriptively compared. We will then compare the change in fasting glucose and weight at Visit 2 (Baseline/Initial Treatment) and Visit 3 (Final Treatment/Safety). In the event of an early withdrawal, measures taken at the early withdrawal visit will be used in place of Visit 3 data. We will descriptively note if any dosing group was more inclined to experience one or both of these safety events. In a similar fashion, if we notice a significant ‘spike’ associated with a particular dosing group, we’ll construct a chi-square test to see if it is statistically significant.

Secondarily, we will report the incidence of mild, moderate, and severe hypoglycemia overall and by group. Mild hypoglycemia will be defined as $54 \text{ mg/dL} \leq \text{fasting glucose} < 70 \text{ mg/dL}$; moderate hypoglycemia is $40 \text{ mg/dL} \leq \text{fasting glucose} < 54 \text{ mg/dL}$; and severe hypoglycemia is $\text{fasting glucose} < 40 \text{ mg/dL}$.

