12.3 Statistical Analysis of Second Aim – efficacy measures

For each of the efficacy outcome measures, we will report mean differences and 95% confidence intervals between Visit 2 (Baseline/Initial Treatment) and Visit 3 (Final Treatment/Safety) for each study group. In the event of an early withdrawal, measures taken at the early withdrawal visit will be used in

place of Visit 3 data, if possible. Possible trends in cognitive function, motor function, and mood and apathy scores will be addressed.

We will look at the individual components and domains assessed by the chosen cognitive, motor, mood, and apathy measures to determine if any appear to be more sensitive to IN insulin. We will also explore the data for components that have a larger dose response. That is, they increase or decrease as the dose-level increases.

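### Section 12.2 treats the ordered doses as unordered groups for every primary safety endpoint; an exploratory dose trend would add a modest gain at almost no cost

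*Combined protocol and SAP*

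**What the plan says.** The primary objective, in the Protocol Summary and section 3.1, is "To determine the safety and tolerability of three different doses of intranasal insulin". Section 5 opens: "This study is a single center trial to determine dose finding, safety and tolerability of 3 doses of intranasal (IN) regular insulin". The Protocol Summary classes the study as dose-finding and lists "Dose 1, group with 7 participants: 20 IU/IN", "Dose 2, group with 7 participants : 40 IU/IN" and "Dose 3, group with 9 participants: 80 IU/IN", with a fourth group of 7 on placebo.

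Section 12.2 begins: "To assess safety and tolerability of the study drug at varying dose levels, AEs and SAEs will be categorized and summarized by study group". The composite event (low fasting glucose or unintended weight loss) is counted per group and compared descriptively. Change in fasting glucose and in weight is compared between Visits 2 and 3, with no dose term. A chi-square test follows only if one dosing group is noticed to stand out. The section does not say whether that test is pairwise or across all four arms.

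Section 12.1 supplies the general methods. For continuous data, t-tests or Mann-Whitney tests "are used to compare the difference of a continuous measure between groups"; for categorical data, chi-square tests are used. None of these uses the order of the doses.

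The only dose-response statement is in section 12.3, for efficacy: "We will also explore the data for components that have a larger dose response". Sections 12.1 and 12.4 call the analysis mainly exploratory and descriptive, and section 12.4 sets no power target.

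**The concern.** Whether harm rises with dose is a central safety question in a dose-finding trial. The plan looks for a gradient in its secondary aim but not in its primary one. With 30 participants, the order of the arms is information that costs nothing to use.

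The trigger for testing adds to this. It looks for one group out of line, whereas a steady gradient need not produce one and so may prompt no test. A real gradient in glucose, weight or adverse events could then be read as no signal.

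**Working it through.** **Inputs from the documents.** Daily doses follow from Table 2: 10 IU × 1 nostril × 2 = 20; 10 × 2 × 2 = 40; 20 × 2 × 2 = 80; placebo 0. Arm sizes in dose order are 7, 7, 7, 9 (total 30). The plan gives no power, alpha, SD or event rate, so it has no figure to reproduce.

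**Assumptions.** Two-sided 5%; effects in SD units of the change score; event risks as shown.

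**Continuous endpoints.** Mean dose = (0 + 140 + 280 + 720)/30 = 38. Sum of squares S = 7·38² + 7·18² + 7·2² + 9·42² = 10,108 + 2,268 + 28 + 15,876 = 28,280.

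- Trend noncentrality: Σ nᵢ(dᵢ − 38)μᵢ/√S. For a linear effect of 1 SD at 80 IU this is √28,280/80 = 2.10. Power is 53% on either 26 or 28 df.
- 80 IU v placebo t-test: 1/√(1/7 + 1/9) = 1.98 on 14 df, power 46%. With the variance pooled over all arms it is about 48%.
- Four-arm F-test: λ = Σ nᵢ(μᵢ − μ̄)² = 28,280/6,400 = 4.42 on (3, 26) df, power 34%.

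Other shapes, each with a 1 SD effect where present:

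| Shape | Trend noncentrality | Trend | 80 IU v placebo | Four-arm F |
|---|---|---|---|---|
| Linear | 2.10 | 53% | 46% | 34% |
| 80 IU only | 378/168.2 = 2.25 | 58% | 46% | 47% |
| 40 and 80 IU | 392/168.2 = 2.33 | 61% | 46% | 55% |
| Full effect from 20 IU | 266/168.2 = 1.58 | 33% | 46% | 41% |
| 40 IU only | 14/168.2 = 0.08 | 5% | 5% | 41% |

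If the peak at 40 IU comes with half the effect at 20 IU, the trend has 6% and F has 39%.

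**Binary endpoints.** All 8 × 8 × 8 × 10 = 5,120 outcomes were enumerated. The exact conditional trend test (scores 0/20/40/80) was set against the exact four-group Fisher-Freeman-Halton test.

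| Assumed risks at 0/20/40/80 IU | Exact trend | Exact four-group |
|---|---|---|
| 10/20/35/60% | 60% | 40% |
| 15/20/30/50% | 34% | 20% |
| 2/5/10/20% | 17% | 9% |
| 2/3/5/10% | 4% | 3% |
| 10/50/50/50% (plateau) | 19% | 29% |
| 40/20/30/60% (raised on placebo) | 20% | 23% |

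The fourth row is near zero because only 7(0.02 + 0.03 + 0.05) + 9(0.10) = 1.6 events are expected. Two events, both at 80 IU, give an exact trend p of C(9,2)/C(30,2) = 36/435 = 0.083. Three, all at 80 IU, give C(9,3)/C(30,3) = 84/4,060 = 0.021. With fewer than three events the test cannot reach 5%.

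**An example of what the plan could miss.** Suppose events are 0/7, 1/7, 2/7 and 4/9 by rising dose. The exact trend gives p = 0.036, the four-arm chi-square 4.80 on 3 df (p = 0.19), and Fisher's test of 80 IU against placebo p = 0.088.

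**Volume.** Table 2 lists 200 µl for placebo and for 80 IU, and 100 µl for 20 and 40 IU. It does not say whether this is per nostril or per administration. On either reading placebo matches the top dose (both use both nostrils), so volume is not monotone in dose once placebo is scored 0.

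**The case against.** The strongest reply is that the plan relies on no hypothesis test. It is expressly descriptive, sets no alpha or decision rule and disclaims power. By-group tables ordered by dose let a reader see a gradient, and each dose's own event count matters directly for naming a safe dose. This stands as far as it goes: no planned analysis is wrong. It does not remove the point, because a slope with a confidence interval is itself a descriptive summary, and the plan already foresees tests on safety data.

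A reader might infer that dose-related harm is judged only by comparing pairs of arms, 14 to 16 people at a time. Section 12.2 does not support this. A four-arm chi-square would use all 30; what it would still ignore is the order.

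A reader might also infer that a trend is better in nearly every case. It is not. It loses under a plateau from 20 IU and almost entirely under a peak at 40 IU. It also gains little for rare events, and the protocol expects hypoglycemia to be rare: section 1.1.5 cites a review of 1,092 people with no symptomatic hypoglycemia and no serious events.

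Finally, section 1.1.5 names local nasal irritation as the most common side effect. Volume-related events on placebo could hide a dose trend in any AE, as the 40/20/30/60% row shows. That objection stands and shapes the fix.

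**Conclusion.** The point holds as a modest efficiency gain and a matter of internal consistency: a dose-finding trial explores dose response for efficacy but not for its primary safety endpoints. If harm is monotone in dose, a trend gains about 7 points of power over 80 IU against placebo (about 5 with pooled variance) and 18 to 19 over a four-arm F-test in the linear 1 SD case. It gains about 20 points over an exact four-group test at risks of 10/20/35/60%. These sizes rest on assumed effects, risks and alpha, none of which the documents give. For the composite event and SAEs, if rare, the practical gain is close to nil.

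It would be wrong to conclude that the planned analysis is invalid or that the trial's conclusion fails. The by-group summaries are needed in any case.

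**What to change.** In section 12.2, add one prespecified dose-trend analysis per primary safety endpoint, labelled exploratory, over all randomised participants with placebo as dose 0:

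- Change in fasting glucose and in weight: linear slope per 20 IU/day with a 95% CI.
- Participants with the composite event, and with any AE: exact Cochran-Armitage test with scores 0/20/40/80. Describe SAEs only, or use the same test if at least three participants have one.
- By-group estimates beside each trend, so that a plateau or mid-dose pattern stays visible.
- Nasal and local AEs reported separately, and the AE trend repeated without them.
- As a sensitivity analysis, the trend in the three insulin arms alone. This is weaker: over 23 participants S = 71,600 − 1,140²/23 = 15,096, so the noncentrality for the linear 1 SD case falls from 2.10 to √15,096/80 = 1.54.

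Also state whether any chi-square test is pairwise or four-arm.

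The cost is SAP wording and a few lines of code, with no new data, visits or participants. The downside is lower sensitivity than by-group tests when the dose response is not monotone, which is why the by-group estimates must stay.

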1 INTRODUCTION

1.1 Background/Rationale

Parkinson's disease (PD) is the second most common neurodegenerative disease after Alzheimer's dementia and was originally described as a motor disease (Parkinson, 1817). The diagnosis of PD is still based on the core motor features of bradykinesia, resting tremor, and rigidity (Postuma et al., 2015), primarily as a result of degeneration of nigrostriatal dopaminergic neurons. In addition to the classic motor symptoms, however, PD is increasingly recognized as a multisystem disorder. A variety of non-motor symptoms, including cognitive deficits and dementia, are commonly observed in patients with PD (Aarsland et al., 2017).

1.1.1 PD and Cognition

Strong evidence indicates that in comparison with age-matched groups without PD, people with PD exhibit more rapid decline in a number of cognitive domains — in particular, executive, attentional and visuospatial domains, but also memory. The full spectrum of cognitive abilities can be observed in PD, from normal cognition, through early mild subjective and objective decline (mild cognitive impairment (MCI)), to mild, moderate and even severe PD dementia (PDD).

Cognitive impairment might occur very early in the course of PD, sometimes even before the onset of motor symptoms. Among PD patients without dementia, approximately 25–30% have MCI, which is evident at the time of diagnosis in 10–20% of patients (Svenningsson et al., 2012). Presence of MCI is associated with a shorter time to progression to a dementia diagnosis, although considerable variability is observed, with some patients remaining stable and a few even reverting to normal cognition (Pedersen et al., 2013).

PD dementia is particularly prevalent in the advanced stages, resulting in high morbidity and mortality. Several long-term longitudinal studies have indicated that the majority of patients with PD will develop dementia if they survive for more than 20 years after diagnosis (Hely et al., 2008). On the basis of numerous studies, it has been documented that dementia in PD has important adverse implications for functioning, quality of life, caregiver burden, and health-related costs (Aarsland et al., 2017).

1.1.2 PD and Insulin

Historically insulin was thought solely to be a peripherally acting hormone responsible for glucose homeostasis and energy metabolism. However, accumulating evidence indicates insulin can cross the blood-brain-barrier and influence a multitude of processes in the brain including regulating neuronal survival and growth, dopaminergic transmission, maintenance of synapses and pathways involved in cognition (Athauda and Foltynie, 2016).

Multiple research studies have identified links between PD and type 2 diabetes mellitus (T2DM), particularly highlighting associations between Parkinson's disease pathogenesis and the mechanisms underlying the development of insulin resistance. A recent large cohort study by De Pablo-Fernandez et al. (De Pablo-Fernandez et al., 2018), reported an increased rate of subsequent PD in T2DM, suggesting a shared genetic predisposition and/or disrupted shared pathogenic pathways.

Both insulin and glucagon-like peptide 1 agonists (GLP-1) have previously been found to have neuroprotective effects in animal models of synucleinopathies, including PD and multiple system atrophy (Bassil et al., 2017), possibly due to effects on neuronal survival and growth, maintenance of

synapses, and dopaminergic transmission. Insulin deficiency or resistance has been implicated in the pathogenesis of several neurodegenerative diseases (Jankovic, 2017).

A review article by Aviles-Olmos et al. (2013) highlights varying associations between diabetes or abnormal glucose tolerance and sporadic forms of Parkinson's disease from both cross-sectional and cohort studies. Survey data reveal that diabetes is established in 8–30% of patients with PD, consistently in excess of the prevalence found in non-Parkinson's disease individuals (Chalmanov and Vurbanova, 1987; Pressley et al., 2003). Another investigation found no link between the two diseases: A meta-analysis of 14 studies comprising a total of 21,395 patients with PD and 84,579 individuals without PD found a negative association between T2DM and PD (Lu et al., 2014).

A case control study showed that patients with PD dementia had a higher prevalence of abnormal glucose metabolism, mainly insulin resistance, than non-demented patients with PD (Bosco et al., 2012). Another study found that patients with PD and comorbid DM exhibited increased impairment in attentional function and executive function deficits than PD patients without DM (Ashraghi et al., 2016).

Several discoveries have highlighted common cellular pathways that potentially relate neurodegenerative processes with abnormal mitochondrial function and abnormal glucose metabolism. This includes converging evidence identifying that peroxisome proliferator activated receptor gamma coactivator 1- α (PGC1 α), a key regulator of enzymes involved in mitochondrial respiration and insulin resistance, is potentially pivotal in the pathogenesis of neurodegeneration in Parkinson's disease (Ashraghi et al., 2016; Sandyk, 1993). Other studies suggested that the insulin- or IGF-1-activated PI3K/Akt/GSK3 β signaling pathway may be involved in PDD pathogenesis (Yang et al., 2018).

Besides in PD, increased insulin resistance and glucose intolerance has been observed in a multitude of neurodegenerative processes including Alzheimer's disease (Craft, 2006), and Huntington's disease (Saleh et al., 2010).

